16.1 Pharmacokinetics

PK evaluation will be performed by PPD [REDACTED].

All statistical analyses and descriptive summaries of PK data will be performed on the PK Analysis Set.

16.1.1 Descriptive Statistics of PK Concentration Data

PK measurements of tepotinib and its metabolites CCI [REDACTED] in plasma will be descriptively summarized by day using: number of non-missing observations (n), arithmetic mean (Mean), standard deviation (SD), coefficient of variation (CV%), minimum (Min), median (Median) and maximum (Max).

Descriptive statistics will only be calculated for n>2 in which a measurement of below lower limit of quantification (BLQ) represents a valid measurement and will be taken as zero for summary statistics of PK concentration data.

Any mean or median value that is below the lower limit of quantification will be shown as BLQ.

Descriptive statistics of PK concentration data will be calculated using values with the same precision as the source data and rounded for reporting purposes only. In export datasets, as well as in the SDTM PC domain, PK concentrations will be provided with full precision and will not be rounded.

The following conventions will be applied when reporting descriptive statistics of PK concentration data:

n	0 decimal place
Mean, Min, Median, Max:	3 significant digits
SD:	4 significant digits
CV%:	1 decimal place

16.1.2 Descriptive Statistics of PK Parameter Data

PK parameter data of tepotinib and CCI [REDACTED] CCI [REDACTED] on Day 1 and 12 will be descriptively summarized by day using: number of non-missing observations (n), arithmetic mean (Mean), standard deviation (SD), coefficient of variation (CV%), minimum (Min), median (Median), maximum (Max), geometric mean (GeoMean), the geometric coefficient of variation (GeoCV) and the 95% confidence interval for the GeoMean (LCI 95% GM, UCI 95% GM). For PK parameters related to time (e.g. tmax, tlag, tlast), only n, Min, Median, and Max may be reported.

Descriptive statistics will only be calculated for a PK parameter when n>2.

PK parameters read directly from the measurements (i.e. Cmax) will be reported with the same precision as the source data. All other PK parameters will be reported to 3 significant figures. In export datasets, as well as in the SDTM PP domain, PK parameters will be provided with full precision and will not be rounded. Descriptive statistics of PK parameter data will be calculated using full precision values and rounded for reporting purposes only.

The following conventions will be applied when reporting descriptive statistics of PK parameter data:

n	0 decimal place
Mean, Min, Median, Max, GeoMean, 95% CI:	3 significant digits
SD:	4 significant digits
CV%, GeoCV%:	1 decimal place

16.1.3 Statistical Analysis of PK Parameter Data

Analysis of Primary Endpoints

The effect of co-administration of itraconazole on tepotinib exposure will be assessed. A general linear model with a fixed effect for TREATMENT and a random effect for SUBJECT will be applied to the log-transformed PK parameters C_{max} , $AUC_{0-tlast}$ and $AUC_{0-\infty}$ based on the PK analysis set. Treatment differences on the log scale of tepotinib with itraconazole versus tepotinib alone (Day 12 versus Day 1) will be estimated for the C_{max} , $AUC_{0-tlast}$ and $AUC_{0-\infty}$ together with their 90% CIs. Point estimates and CIs will be back transformed to the original scale for presentation.

The analysis will be repeated with both SUBJECT and TREATMENT as fixed effects.

CCI [REDACTED]

[REDACTED]

[REDACTED]

[REDACTED]

The analysis will be repeated with both SUBJECT and TREATMENT as fixed effects.

CCI [REDACTED]

[REDACTED]

[REDACTED]

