AUC _{extra%}	The AUC from time t_{last} extrapolated to infinity given as percentage of $AUC_{0-∞}$. $AUC_{extra\%} = (\text{extrapolated area}/AUC_{0-∞}) \times 100$.
	CCI [REDACTED] [REDACTED] [REDACTED]
	[REDACTED] [REDACTED] [REDACTED]

- Whole blood samples of approximately 2 mL per collection for measurement of plasma concentrations of tepotinib and its CCI CCI will be collected. Collection times are specified in the Schedule of Assessments (Section 1.3) and Table 1. The actual date and time (24-hour clock time) of each sample will be recorded to calculate actual time elapsed since the prior dose administration.
- The quantification of tepotinib and its CCI CCI in plasma will be performed using a validated assay method. Concentrations will be used to evaluate the PK of tepotinib and its metabolites.
- Remaining samples collected for analyses of tepotinib concentration may also be used to evaluate safety or efficacy aspects related to concerns arising during or after the study.
- Details on processes for collection and handling of these samples are in the Laboratory Manual. Retention time and possible analyses of samples after the end of study are specified in the respective ICF.
- PK parameters will be derived using noncompartmental methods with the validated computer program.

The exact date and time of sample collection and study intervention (24-hour clock time) must be recorded in the eCRF and will be used in the calculation of PK parameters. The accepted time deviations from planned tepotinib PK times that will not be considered a protocol violation are listed below (Table 2).

Table 2 PK Sampling Time Windows

Procedure	Time Point (Relative Time)	Window Allowance
Pharmacokinetics	Predose	- 60 min
	1 to 12 hours postdose	- 5 / + 5 min
	> 12 to 24 hours postdose	- 30 / + 30 min
	> 24 to 72 hours postdose	- 60 / + 60 min
	> 72 to 168 hours postdose	- 180 / + 180 min

Any deviation from the above-mentioned time windows requires a comment in the eCRF and may be discussed in the data review meeting.

Collection of Feces for Pharmacokinetic Analysis

In both in-house periods of the study, all feces after administration of tepotinib until discharge from the CRU (i.e., from Day 1 to Day 4, and from Day 12 to Day 15) will be collected for exploratory tepotinib pharmacokinetic analysis.

- To ensure defecation, participants will receive a mild laxative on the evenings of Day 3 and Day 14.

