9.3 Analyses Sets

The analysis sets are specified below. The final decision to exclude participants from any analysis sets will be made during a data review meeting prior to database lock.

Analysis Set	Description
Screening (SCR)	All participants, who provided informed consent, regardless of the participant's enrollment and study intervention status in the study.
Safety (SAF)	All participants, who were administered any dose of any study intervention. Analyses will consider participants as treated.
Pharmacokinetic (PK)	The PK Analysis Set is a subset of the SAF, and the PK population will include all participants: Who have completed the study without any relevant protocol deviations and factors likely to affect the comparability of PK results. With adequate study intervention compliance. With evaluable PK data, i.e., nonmissing values for primary endpoints. If participants received prohibited concomitant therapy or medicines, as specified in Section 6.8.3, they will be excluded from the PK population. All PK analyses will be based on this analysis set.

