8.1 Definition of Analysis Sets

Analysis Set	Description
Screening (SCR)	All participants, who provided informed consent, regardless of the participant's enrollment and study intervention status in the study.
Safety (SAF)	All participants, who were administered any dose of any study intervention. Analyses will consider participants as treated.
Pharmacokinetic (PK)	The PK Analysis Set is a subset of the SAF, and the PK population will include all participants: Who have completed the study without any relevant protocol deviations and factors likely to affect the comparability of PK results. With adequate study intervention compliance. With evaluable PK data, i.e., non-missing values for primary endpoints. If participants received prohibited concomitant therapy or medicines, as specified in Section 6.8.3 of the CSP, they will be excluded from the PK population. All PK analyses will be based on this analysis set.

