10.2 Protocol Deviations / Exclusion from Analysis Sets

10.2.1 Important Protocol Deviations

Listings of important protocol deviations will be provided including the date and relative day in relation to first dosing in the study. A distinction will be made between important protocol deviations due to COVID-19 versus not due to COVID-19. The respective important protocol deviations will be flagged accordingly.

Important protocol deviations or important events that might have an effect on PK include, but may not be limited to the following:

- Adverse events like diarrhea etc. (these instances will be discussed on a case-by case basis)
- Vomiting after administration following oral dosing (these instances will be discussed in alignment with applicable regulatory guidelines on a case-by case basis)
- Sample processing errors that may lead to inaccurate bioanalytical results
- Inaccurate dosing or dosing errors (e.g. dose administration delayed, dose change or missed doses)
- Pre-dose or trough sample collected after the actual dosing
- Non-compliance with food and drink requirements (e.g. non-fasted, incomplete meal consumption, caffeine intake)
- Concomitant medication, vitamins, dietary or herbal supplements

Should one or more of these events be available at the Data Review Meeting, its implication for PK evaluation will be discussed and agreed amongst relevant study team members (e.g. Sponsor Clinical Pharmacology/Biostatistics/Clinical Pharmacokinetics & Pharmacodynamics team representative). Appropriate action will be taken such as flagging individual values to be excluded from analysis.

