16.1.4 General Specifications for PK Concentration and PK Parameter Data

Predose samples that occur before the first drug administration will be assigned a time of 0 hours, as if the sample had been taken simultaneously with the study intervention administration. Same applies to the pre-dose sample after multiple doses.

Predose or trough samples which have been taken after the subsequent dosing will be reported as a protocol deviation. The resulting concentrations will be included in concentration listings but excluded from descriptive statistics of concentrations and from PK parameter estimation.

Values BLQ will be taken as zero for summary statistics of PK concentration data, PK parameter estimation (e.g. AUC) and for graphical presentations.

Missing concentrations (e.g. no sample, insufficient sample volume for analysis, no result or result not valid) will be reported and used generally as “N.R.”. A participant who withdraws prior to the last planned observation will be included in the analyses up to the time of discontinuation if still included in the PK analysis set.

If samples are collected outside of 10% of the PK sampling time windows defined in the CSP in section 8.4, these will be included in the PK parameter estimation (NCA) but will be excluded from the concentration summary and mean/median concentration plots.

PK concentrations which are erroneous due to a sampling processing or analytical error (as documented in the bioanalytical report) may be excluded from the PK analysis if agreed by the Sponsor. In this case the rationale for exclusion will be provided in the CSR. Any other PK concentrations that appear implausible to the Clinical Pharmacologist/Clinical PK/PD Scientist will not be excluded from the analysis. Any implausible data will be documented in the CSR.

If important protocol deviations occurred likely to affect the PK profile of participants as specified in Section 10.2.1, the impacted concentrations and PK parameters will be excluded from summary statistics and further statistical evaluation.

Any PK concentrations or PK parameters excluded from summary statistics will be included in participants listings and flagged; a reason for exclusion will be detailed in the CSR (e.g. a footnote or a table of exclusions). Any flags should be included in the study specific CDISC data sets.

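### Is the tepotinib ratio left unprotected against adverse-event exclusions because the fixed-SUBJECT repeat cannot detect them?

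*SAP*

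**What the plan says.** The primary model has TREATMENT fixed and SUBJECT random, on log Cmax, AUC0-tlast and AUC0-inf, comparing Day 12 with Day 1 (SAP 16.1.3, Protocol 9.4.3). Then: "The analysis will be repeated with both SUBJECT and TREATMENT as fixed effects".

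SAP 8.1 admits to the PK set participants "Who have completed the study without any relevant protocol deviations and factors likely to affect the comparability of PK results" and "With evaluable PK data, i.e., non-missing values for primary endpoints".

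On timing, Protocol 9.3 states: "The final decision to exclude participants from any analysis sets will be made during a data review meeting prior to database lock". SAP 6 and Protocol 9.4.4 place the planned analyses after lock.

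SAP 10.2.1 lists events that may affect PK. Diarrhea is to be discussed case by case; vomiting likewise, but in line with regulatory guidelines. The outcome: "Appropriate action will be taken such as flagging individual values to be excluded from analysis". SAP 16.1.4 says that where important deviations likely to affect the PK profile occurred, "the impacted concentrations and PK parameters will be excluded from summary statistics and further statistical evaluation". The same section keeps concentrations that merely look implausible and requires excluded values to be flagged, with a reason given in the study report. SAP 16.1.6.1 lists individual PK parameters on the Safety Analysis Set.

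Protocol 8.4 adds a feature of conduct: "To ensure defecation, participants will receive a mild laxative on the evenings of Day 3 and Day 14".

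**The concern.** A repeat of the primary analysis looks like a robustness check. Here it changes the model and not the data, so it cannot reveal whether dropping participants or values moved the ratio. The only other visible sensitivity analysis (SAP 16.1.5.1) is optional and removes further data.

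Adverse-event exclusions are also foreseeable. The risk table in Protocol 2.3.1 calls diarrhea, nausea and vomiting common with tepotinib, a laxative falls inside both sampling periods, and diarrhea has no severity or timing criterion of its own. If itraconazole raises exposure, exposure-related events would cluster after Day 12, and removing those profiles would pull the ratio down. Removing low profiles, such as a vomited dose, would push it up. The study is open-label, and no visible text keeps concentrations from the meeting that decides. At stake would be a biased interaction ratio with nothing in the report to show it.

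**Working it through.** **1. The plan's precision figure, and the yardstick.** Protocol 9.2 gives 0.805 to 1.242 for N = 14, CV 20%, ratio 1. With s = sqrt(ln(1 + 0.20²)) = 0.198:

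exp(±t(0.95; 12) × s × sqrt(4/14) × sqrt(chi²(0.80; 12)/12)) = exp(±1.782 × 0.198 × 0.535 × 1.148) = exp(±0.217) = 0.805 to 1.242.

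The figure reproduces with a two-group variance. The paired form (variance factor 2/14, 13 df) gives 0.859 to 1.164, so the stated precision is wider than the paired design implies. For scale I use the expected paired 90% CI at CV 15%, s = 0.149: exp(±1.771 × 0.149 × sqrt(2/14)) = 0.905 to 1.105, about ±10%.

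**2. What the repeat does on complete pairs.** Both models estimate the log ratio as the mean within-participant difference. In a simulated trial (N = 14, CV 15%; between-participant log SD 0.35 and true ratio 1.2 assumed), both give 0.180609 with SE 0.049853. Over 100 such trials the estimates never differ to six decimals. The repeat is therefore silent on exclusions.

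**3. What it does when one day is missing.** Dropping two single-day values from that trial but keeping the participants gives 0.158939 with SUBJECT random and 0.170414 with SUBJECT fixed. Deleting those participants altogether also gives 0.170414. So if a participant with one evaluable day stays in, the random model uses the leftover value and the fixed repeat equals the complete-pairs answer. The planned pair of analyses then shows both treatments of that value.

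**4. How far exclusions could move the ratio.** Inputs: 18 dosed (Protocol 9.2), within-CVs from Protocol Table 4, a common treatment effect, and between-participant CV 35% (not in the documents). Log Day 1 = b + e1; log Day 12 = b + effect + e2; each SD = sqrt(ln(1 + CV²)). The shift is exp(mean retained log ratio − effect) − 1, averaged over simulated trials on the log scale. In the one-day row it is the random-SUBJECT estimate against the full-data estimate.

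| What is excluded (one / two) | CV 15% | CV 20% |
|---|---|---|
| Participants, odds of exclusion doubling per SD of Day 12 log exposure | -0.2% / -0.5% | -0.4% / -0.8% |
| Participants with exactly the highest Day 12 exposure | -0.6% / -1.2% | -1.1% / -2.0% |
| Highest Day 12 value only, Day 1 kept, random SUBJECT | -1.2% / -2.3% | -1.9% / -3.6% |
| Participants with exactly the highest individual ratios | -2.2% / -4.1% | -3.0% / -5.4% |

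Varying the assumed between-CV from 25% to 50% moves the second row's -2.0% to between -2.4% and -1.5%. Adverse events track exposure imperfectly, so the first row is the more realistic kind of selection; the others are extremes. All are small against ±10%.

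**5. Order of decisions.** Exclusion from an analysis set is decided before lock (Protocol 9.3), and the events in SAP 10.2.1 are discussed at the same data review meeting. The treatment ratio is computed after lock. The planned ratio should therefore not exist when exclusions are decided.

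**6. The laxative.** Tepotinib is given on the mornings of Days 1 and 12 (Protocol 5.3.1). The laxative comes on the evenings of Days 3 and 14, about 2 × 24 + 12 = 60 hours later, well past the dense 1 to 16 hour sampling in Protocol Table 1. It is the same in both periods and so gives no reason for exclusions to fall more on one day.

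**The case for a change.** The strongest reply has three parts.

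First, timing relative to lock does not hide individual results. Judging whether primary endpoints are non-missing means that the availability of PK results is known, the study is open-label, and the bar on dropping implausible values does not cover an adverse-event exclusion made with the value in view. This stands as a gap in the visible text. What it could do at worst can be bounded: if all four spare participants (18 to 14) were removed and were exactly the four with the highest ratios, the ratio would fall by about 7.4% at CV 15%. That requires selection on the ratio itself, which nothing in the plan calls for. SAP 16.1.4 ties value exclusion to deviations likely to affect the PK profile and demands flags and reasons, so such selection would be visible in the listings.

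Second, SAP 16.1.3 does not say whether a participant with one evaluable day stays in the model, and SAP 9.4 assumes missing data are completely at random. The rule is unstated, but step 3 shows that its consequence would be on display.

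Third, a supportive run with excluded data restored would be cheap. It would also bring distortion of its own. At N = 16, keeping one vomited dose that lost 30% to 50% of exposure (assumed) shifts the ratio by exp(ln(0.7)/16) − 1 = -2.2% to exp(ln(0.5)/16) − 1 = -4.2%. That exceeds the whole-participant shifts for exposure-linked exclusion that it would be checking. Redacted text directly after the quoted sentence may also already contain such a run.

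**Conclusion.** The concern does not hold. It is true that on complete pairs the fixed-SUBJECT repeat adds nothing about exclusions, but the plan never assigns it that purpose. It is not true that nothing guards the exclusions: decisions precede lock, planned analyses follow it, implausibility alone is no ground for removal, value exclusion needs a likely PK effect, and excluded values are flagged and listed so that a reader can recompute the ratio where parameters were derived.

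Followed as written, the plan gives a sound descriptive ratio (Protocol 9.1 plans no hypothesis tests). For one or two exposure-linked participant exclusions the expected shift at CV 15% is about -0.2% to -0.5%, and -0.6% to -1.2% if they fall on exactly the highest Day 12 exposures, against a 90% CI of about ±10%. These sizes rest on 18 dosed, a common treatment effect and the assumed 35% between-participant CV; the direction in practice is unknown. What remains is unstated detail on the order of decisions and on participants with one evaluable day. Stating it would be a matter of preference, not the correction of a rule shown to mislead.

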16.1.4 General Specifications for PK Concentration and PK Parameter Data

Predose samples that occur before the first drug administration will be assigned a time of 0 hours, as if the sample had been taken simultaneously with the study intervention administration. Same applies to the pre-dose sample after multiple doses.

Predose or trough samples which have been taken after the subsequent dosing will be reported as a protocol deviation. The resulting concentrations will be included in concentration listings but excluded from descriptive statistics of concentrations and from PK parameter estimation.

Values BLQ will be taken as zero for summary statistics of PK concentration data, PK parameter estimation (e.g. AUC) and for graphical presentations.

Missing concentrations (e.g. no sample, insufficient sample volume for analysis, no result or result not valid) will be reported and used generally as “N.R.”. A participant who withdraws prior to the last planned observation will be included in the analyses up to the time of discontinuation if still included in the PK analysis set.

If samples are collected outside of 10% of the PK sampling time windows defined in the CSP in section 8.4, these will be included in the PK parameter estimation (NCA) but will be excluded from the concentration summary and mean/median concentration plots.

PK concentrations which are erroneous due to a sampling processing or analytical error (as documented in the bioanalytical report) may be excluded from the PK analysis if agreed by the Sponsor. In this case the rationale for exclusion will be provided in the CSR. Any other PK concentrations that appear implausible to the Clinical Pharmacologist/Clinical PK/PD Scientist will not be excluded from the analysis. Any implausible data will be documented in the CSR.

If important protocol deviations occurred likely to affect the PK profile of participants as specified in Section 10.2.1, the impacted concentrations and PK parameters will be excluded from summary statistics and further statistical evaluation.

Any PK concentrations or PK parameters excluded from summary statistics will be included in participants listings and flagged; a reason for exclusion will be detailed in the CSR (e.g. a footnote or a table of exclusions). Any flags should be included in the study specific CDISC data sets.

PK concentrations and PK parameters excluded from summary statistics will not be included in mean/median figures. Mean plots will only contain values where $n > 2$.

CCI

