1.1 Synopsis

Protocol Title: Phase I, Open-label, Single-sequence, Cross-over Study of the Effect of Multiple Doses of Itraconazole on Single-dose Tepotinib Pharmacokinetics in Healthy Participants

Short Title: Tepotinib Drug-Drug Interaction Study With Itraconazole in Healthy Participants

CCI

Objectives and Endpoints:

Objectives	Endpoints	Ref #
Primary		
To investigate the effect of multiple doses of itraconazole on tepotinib PK in healthy participants	
Plasma tepotinib: $AUC_{0-\infty}$, $AUC_{0-t_{last}}$, and C_{max}	1
Secondary		
To assess the safety and tolerability of tepotinib when administered together with itraconazole in healthy participants	
Nature, occurrence, severity, and seriousness of TEAEsAbsolute values and changes in safety laboratory testsSingle 12-lead ECGs evaluated by InvestigatorVital signs assessed from time of first dose to end of study participation	2
To characterize the effect of multiple doses of itraconazole on additional tepotinib PK parameters in healthy participants	
Plasma tepotinib: CL/F, V_z/F, t_{max}, and $t_{1/2}$	3

ECG=electrocardiogram, PK=pharmacokinetics, TEAE=treatment emergent adverse events.

Overall Design: This will be a nonrandomized, open-label, single-sequence, cross-over Phase I study in healthy participants.

Brief Summary:

The purpose of this study is to assess the effect of multiple doses of itraconazole on single-dose tepotinib pharmacokinetics in healthy participants. Study details include:

[figure not shown]
- Study Duration: up to 48 days
- Treatment Duration: single dose of tepotinib on Days 1 and 12, 11 days of treatment with itraconazole (Days 8 to 18)
- Visit Frequency: residence in the Clinical Research Unit from Days -1 to 4 and Days 11 to 15, ambulatory daily visits from Days 5 to 10 and 16 to 20

Number of Participants: A maximum of 18 participants will be assigned to study interventions such that at least 14 evaluable participants complete the study.

Study Intervention Groups and Duration: 21 days of intervention period including Safety Follow Up on Day 20; single dose of tepotinib on Days 1 and 12, 11 days of treatment with itraconazole (Days 8 to 18).

Involvement of Special Committee(s): No

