Study Day	1	2	3	4	5	6	7	8	Notes
	12	13	14	15	16	17	18	19	
Timing PK blood sampling	Predose ^a and 1, 1.5, 2, 3, 4, 6, 8, 12, and 16 hours postdose	24, 30, 38 hours	48, 60 hours	72 hours	96 hours	120 hours	144 hours	168 hours	a Within 60 minutes before tepotinib dosing. All other samples to be collected post tepotinib dose. For PK sampling window allowance see Table 2.

PK=pharmacokinetics.

2 Introduction

Tepotinib (Tepmetko®) is a highly selective, reversible ATP-competitive inhibitor of the receptor tyrosine kinase MET in clinical development for the treatment of patients with e.g., advanced NSCLC with METex14 skipping alterations or MET amplification.

Detailed information on the chemistry, pharmacology, efficacy, and safety of tepotinib is in the IB (current version).

There is extensive clinical experience in the use of itraconazole. It was approved in the United States in 1992 (www.accessdata.fda.gov) and is widely used as antifungal agent. Full information about the potential side effects of itraconazole administration is described in its currently approved SmPC and USPI (refer to [Itraconazole SmPC](#) and [USPI](#)).

CCI

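### Any tepotinib left from the Day 1 dose can only raise the Day 12/Day 1 exposure ratios, and the visible SAP neither checks nor corrects for it

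*SAP*

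**What the plan says.** The order of treatments is fixed. The protocol synopsis gives "single dose of tepotinib on Days 1 and 12, 11 days of treatment with itraconazole (Days 8 to 18". The primary model (Protocol 9.4.3, SAP 16.1.3) compares Day 12 with Day 1 for log Cmax, AUC0-tlast and AUC0-∞, with TREATMENT fixed and SUBJECT random. The only visible variation on it is "The analysis will be repeated with both SUBJECT and TREATMENT as fixed effects".

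A predose sample is scheduled on both tepotinib days (Protocol Table 1: "Within 60 minutes before tepotinib dosing"). SAP 16.1.4 says how it is used:

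- "Predose samples that occur before the first drug administration will be assigned a time of 0 hours", and then "Same applies to the pre-dose sample after multiple doses".
- "Values BLQ will be taken as zero for summary statistics of PK concentration data, PK parameter estimation (e.g. AUC) and for graphical presentations". A quantifiable Day 12 predose value is therefore used as measured.
- "Any other PK concentrations that appear implausible to the Clinical Pharmacologist/Clinical PK/PD Scientist will not be excluded from the analysis".

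The PK Analysis Set (SAP 8.1) takes participants "Who have completed the study without any relevant protocol deviations and factors likely to affect the comparability of PK results". SAP 10.2.1 sends events that may affect PK to the Data Review Meeting; its list is open-ended and does not name a quantifiable Day 12 predose. The one sensitivity analysis visible in SAP 16.1.5.1 concerns AUCextra% and adjusted R². The visible text contains no washout rationale, predose/Cmax criterion, subtraction or carry-over analysis.

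**The concern.** No tepotinib is present before the Day 1 dose, and a residual cannot be negative. Carry-over therefore enters only the numerator of each ratio, always upward. Because period and treatment coincide, no model term can separate the two. When everyone has both periods, as the PK Analysis Set requires, the random-SUBJECT and fixed-SUBJECT models both estimate the mean within-participant log difference, so the repeat is no check.

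Itraconazole covers the last 96 h before the second tepotinib dose. If it slows systemic clearance, it also preserves more of the Day 1 residual, so the bias tends to grow with the interaction being measured. The analysis is descriptive (Protocol 9.1), so the reported ratio is itself the result, and enrolling more participants would not reduce this error.

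**Working it through.** **Inputs.** Doses on Days 1 and 12 are 11 × 24 = 264 h apart. Itraconazole starts on Day 8, 7 × 24 = 168 h after the first dose, leaving 264 − 168 = 96 h under inhibition. Sampling ends at 168 h (Protocol Table 1). AUCextra above 20% is flagged (SAP 16.1.5.1). Protocol 2.3.1 gives a worst-case P-gp share of 30% of clearance and at most 25% of the dose for any single metabolic pathway. Half-life and LLOQ are not given; a range of 32 to 72 h is assumed, its upper end tied to the 20% flag.

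**Plan's own figures first.** 1/(1 − 0.30) = 1.43 reproduces the stated 43% maximum AUC increase. For Table 4 (CV 20%, n = 14, ratio 1.0), s = √ln(1 + 0.20²) = 0.198 and the limits are exp(± t(0.95, df) × SE × √(χ²(0.80, df)/df)). With SE = s√(4/n) and df = n − 2 this gives 0.805 to 1.242, as stated. The within-participant form, SE = s√(2/n) and df = n − 1, gives 0.859 to 1.164. These are the yardsticks for the size of any bias.

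**Carry-over, closed form.** Assume one compartment and linear kinetics, with clearance multiplied by f from Day 8. The fraction of the Day 1 dose left at 264 h is exp(−168λ − 96fλ), where λ = ln 2 / half-life. The residual and the new dose are then cleared at the same rate, so this fraction is also the residual's share of the Day 12 dose's own AUC0-∞. Observed ratio = true ratio × (1 + share). Day 1 AUCextra is exp(−168λ).

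f = 1 is no inhibition. f = 0.70 is the P-gp worst case. f = 1 − 0.30 − 0.25 = 0.45 is an assumed extreme with both pathways lost (ratio 1/0.45 = 2.22).

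| Half-life | Day 1 AUCextra | f = 1 | f = 0.70 | f = 0.45 |
|---|---|---|---|---|
| 32 h | 2.6% | 0.33% | 0.61% | 1.0% |
| 40 h | 5.4% | 1.0% | 1.7% | 2.6% |
| 48 h | 8.8% | 2.2% | 3.3% | 4.7% |
| 60 h | 14.4% | 4.7% | 6.6% | 8.7% |
| 72 h | 19.8% | 7.9% | 10.4% | 13.1% |

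Example, 48 h and f = 1: λ = 0.01444/h, exp(−264 × 0.01444) = 0.022.

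**Noncompartmental check.** Noise-free profiles at the Table 1 times were analysed with the linear-up/log-down rule and best-fit λz, over 33 one- and two-compartment scenarios (half-lives 24 to 80 h, assumed absorption rate 0.25/h). The bias was positive for AUC0-∞, AUC0-tlast and Cmax in all 33. One-compartment AUC0-∞ values were close to the table (2.35% at 48 h, 8.2% at 72 h, f = 1). In a two-compartment case with an 80 h half-life and f = 1, a predose of 4.0% of Cmax went with an 8.3% AUC0-∞ bias, so a small predose percentage does not guarantee a small AUC bias.

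**Is the time-0 rule the source?** Setting only the Day 12 predose value to zero removed at most 0.04 percentage points (2.35% to 2.33% at 48 h, f = 1). Subtracting C0·exp(−λz·t) from the whole profile left at most 0.1% bias in AUC0-∞ in every scenario. The corrected Cmax and AUC0-tlast were not evaluated.

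**Opposing error.** At 32 h and f = 0.70 the true AUC0-∞ ratio is 1.43. The AUC0-tlast ratio, cut at 168 h, is 1.35 before carry-over adds 0.7%.

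**The case against.** The strongest reply is that the bias may be negligible. Up to a 40 h half-life without inhibition it is about 1% or less, small beside the Table 4 limits of 0.805 to 1.242. A reader might take 8 to 13% as the expected error; the documents do not support that. It needs a half-life near 72 h, inferred only from a per-participant diagnostic limit. At 72 h the span-ratio criterion would also need a regression window of 2 × 72 = 144 of the 168 h. The f = 0.45 column assumes full inhibition from the first itraconazole dose, although Protocol 4.3 says four days do not reach steady state, and it puts the whole interaction in systemic clearance. Any part acting on bioavailability would not slow loss of the Day 1 residual. Protocol 2.3.1 rates the CYP3A4 potential as low and the combined effect as unknown. All this stands, and makes the inhibition columns upper bounds.

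A reader might also infer that the predose time assignment causes the bias. It does not: the residual lies under every Day 12 sample. The sentence on implausible concentrations is also not the cause, since a measurable residual is not implausible.

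Nor can one say that no rule exists. Protocol 4.2 and the ends of SAP 16.1.3, 16.1.4 and 16.1.5.1 are redacted and could hold one.

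Finally, the PK Analysis Set wording and the Data Review Meeting allow exclusion, and individual concentrations are listed and plotted. That helps detection. It sets no threshold, relies on judgement in an open-label study, and does not correct the estimate.

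**Conclusion.** The gap is real in the visible text and modest in likely size. Residual tepotinib, if present, raises only the Day 12 values, the model cannot identify it, and nothing visible measures or removes it. Under one-compartment linear decline the AUC0-∞ ratio is inflated by about 0.3%, 1%, 2.2% and 8% at half-lives of 32, 40, 48 and 72 h without inhibition. Under the assumed extreme the figures are at most about 1.0%, 2.6%, 4.7% and 13%. Which applies depends on a half-life and LLOQ that the documents do not give.

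A reader might infer that the total error in the ratios must be upward. Only the carry-over term has a fixed sign; truncating AUC0-tlast at 168 h can act the other way. No decision boundary is at stake, so the effect is on the size of the reported interaction.

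**What to change.** First confirm whether any redacted text already covers a quantifiable Day 12 predose. If not, keep the planned primary analysis and add to SAP 16.1.4/16.1.5.1:

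1. List each participant's Day 12 predose concentration C0, with C0 as a percentage of Day 12 Cmax.
2. If any C0 is quantifiable, derive Day 12 Cmax, AUC0-tlast and AUC0-∞ after subtracting C0·exp(−λz·t), using that participant's Day 12 λz (for AUC0-∞ this removes C0/λz). Repeat the primary model on these values as a prespecified sensitivity analysis.
3. Report the planned and the residual-subtracted ratios side by side with 90% CIs.
4. Identify participants whose Day 12 λz is flagged or not estimable.

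The subtraction belongs in a sensitivity analysis because Cmax and AUC0-tlast otherwise need no λz, and λz is weakest where the residual is largest. A 72 h half-life at f = 0.45 becomes 72/0.45 = 160 h, close to the whole 168 h sampling period. The cost is a few lines of SAP text and some programming, with no new samples. If every C0 is below quantification, the results are unchanged.
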